7. DATA COLLECTION AND MONITORING

7.1 Training and Considerations: All study staff will receive extensive human subjects/research ethics training, including the need for complete confidentiality and to approach questions with sensitivity and in a supportive manner and to provide appropriate referrals when needed. All interviews, surveys and HIV tests will be conducted in private. Study staff will be trained not to press participants to answer questions or engage in intervention activities that seem to be distressing to them, and sessions are terminated if the participant is too distressed, too fatigued, or too frustrated by the effort. Qualitative interviews will be terminated if the participant is too distressed, too fatigued, or too frustrated by the effort. In the event that significant depression symptoms or suicidality are noted, the staff will be instructed to follow procedures in the safety protocol, which include immediately contacting [name] to arrange referral to appropriate service agencies at Mbarara Regional Referral Hospital or within the community, and reporting incidents or concerns to [name] or the US-based PI, [name].

7.2 Privacy and Confidentiality: We will safeguard against loss of confidentiality in a number of ways. To minimize risk during the consent process, all recruitment and consent for participation will be done in a private tent, with closed panels. Individuals will be recruited separately and undergo informed consent separately (regardless of whether they arrived at the healer location with a friend or family member). This will reduce risk of loss of confidentiality as well as risk of coercion from others. All interviews, surveys, and POC HIV testing will take place in private locations. Pretest and post-test counseling will similarly take place in private tents, therefore minimizing risk of loss of confidentiality during relaying of HIV testing results. During the follow up period, study staff will not identify the project as one related to HIV; study staff will contact the participant via mobile phone. They will be instructed not to discuss anything related to the study except with the participant. They may visit the participant's home if unable to contact via phone numbers provided. For this, they will wear unmarked clothes and not speak about HIV or the study with anyone, except in private with the participant.

Loss of confidentiality will also be minimized through de-identification of study data. Only the participant's study ID number will appear in the paper or computer-generated files. The key to participants' code number will be encrypted in a computer file, which will be kept in locked offices at MUST. Only [name] (PI), [name], and the research assistants will be able to unencrypt these computer files. In addition, all study staff will be asked to sign a confidentiality pledge. In signing this pledge, the researcher agrees not to divulge the identity of any study participant outside of the study team, nor discuss the particularities of any participant's story with anyone outside the study team.

Study participants may feel reticent to share information about sexual orientation, and this may be a limitation of our study approach. However, the vast majority of HIV transmission in sub-Saharan Africa occurs through heterosexual intercourse³¹, and therefore we do not anticipate that unwillingness to disclose homosexual orientation will negatively impact our data collection or results. Participants will be reminded during questionnaire administration that answers regarding sexual orientation will be kept between study participant and research team, and that numerous mechanisms are being undertaken to safeguard their identity, including de-identification of study data.

For potential participants for the testing intervention arm who presents with sexual partners, we will carry out private, individual recruitment and consent, and request if we could include the partner in the HIV testing process. If permission is granted by the participant, then we will 1)

assess if the partner meets criteria for inclusion as a participant; 2) if s/he meets inclusion criteria, the participant will undergo informed consent; and 3) we will conduct the remainder of the study procedures with both members of the couple present, and participating. If the partner does not meet criteria for inclusion, then the partner will be present for his/her partner's study procedures. If permission is refused, we will continue with pre-test counseling, testing, relaying of POC HIV test results, and post-test counseling in private. We will specifically train our research assistants to conduct post-test counseling that discusses issues specific to serodiscordant couples, including reducing risk of HIV transmission, reproductive issues and efficacy of PrEP. In addition, we will encourage the participant to disclose to his/her partner, and refer them to the HIV clinic, which has counselors who specifically assist clients with serostatus disclosure strategies and has resources for serodiscordant couples. By following a strict strategy of individual, private consent, our study procedures seek to reduce coercive influences from partners or family members who may be present with the participant.

MUST has completed numerous research studies on human subjects and maintained full confidentiality of participant records over the preceding decade. MUST has close collaborative relationships with the local HIV clinic, with no-cost resources for testing, treatment and counseling; participants will be referred to these resources as necessary over the course of this research. Due to the nature of this research, we will ensure that study staff undergo training on good clinical practices for human subjects research, with extensive piloting of informed consent and study practices, until staff are comfortable and knowledgeable. Specifically, we will train them to identify situations where coercion may be occurring as to avoid placing undue risk on the potential participant. Refresher courses on relevant topics will be carried out as needed, at least once every 6 months.

7.3 Data Safety and Monitoring: No stopping rules have been defined for this project, given the minimal risks to participants. The research procedures are minimally invasive and present low risks to the study participants. Subjects are volunteers and may drop out of the study at any time, without any recourse. They are informed of such during the consent process.

This study is a pilot intervention, so a DSMB is not required. The PI, [name], and local Co-Investigators will review study progress during bi-monthly conference calls. MUST and WCMC IRBs will receive reports annually. Additionally, if necessary, we may utilize the services of the Weill Cornell Medical Center's Data Safety and Monitoring Board (DSMB), which has been designed to ensure the safety and welfare of participants and the validity and confidentiality of data. The board's responsibilities include reviewing protocols, informed consent documents, and plans for data safety and monitoring, evaluating the progress of intervention trials, participant risk versus benefit, periodic assessments of data quality and timeliness, and other factors that can affect the safety of study participants. The board makes recommendations to the PI and NIH (e.g., the observed beneficial or adverse effects of the study, interim analysis of efficacy). The WCMC DSMB meets monthly. The DSMB will receive all adverse event reports and will review stopping rules and interim analyses, where applicable. Data analysis will be conducted every 3 months and discussed with the research team. Annual reports will be submitted to the WCMC IRB, MUST IRB and NIMH.

7.4 Adverse Event Reporting: The Principal Investigator, [name], and the Weill Cornell Medical Center IRB will be directly responsible for monitoring the security of the data and safety of participants. Project staff will report emotionally distressed participants to [name] and [name]. [name] will be responsible for evaluating and referring the participant to an appropriate agency at MUST or in the community. Drs. [name] and [name] will be responsible for immediately reporting any

breaches of protocol, breakdowns in the consent process, violations of confidentiality of the data, complaints by participants or any serious problems or adverse events. An incident report will be filed with [name]. Incident reports, serious problems or adverse events will be reported to the WC IRB by [name]. The IRB will report to NIH and DHHS if warranted. Requests for the use of these data by persons outside of the project will be decided upon by the PI, [name] and a committee comprised of coinvestigators. The IRB will be informed and any concerns will be addressed before data are released.

As participation in this study involves minimal commitment, we do not anticipate any negative impact from study closure or from the subject voluntarily leaving the study. Study subjects will not be terminated for any specific reason. All potentially adverse events or serious problems will be reported by [name] within 48 hours on a standard form and this information will be immediately shared with [name] for reporting to the Weill Cornell IRB with a copy to the Office of Human Subjects. Study staff will also be debriefed on a weekly basis to address issues that have come up throughout the course of data collection. All project staff will receive verbal and written instructions pertaining to the rules governing the maintenance of confidentiality upon completion of the study or if they leave the study before its completion.

7.5 Quality Assurance: The PIs will oversee data quality control and assurance. They will review all informed consent documents and study eligibility checklist forms. [name] and [name] will review data files for internal validity and completeness and send queries to the data management team in Mbarara each week. The team will respond to queries within one week. During the trial, all informed consent and data collection documents will be verified by the study research coordinator.

7.6 Expected Outcomes: The goal of the proposed research is to expand access and engagement with HIV testing in Mbarara by delivering point of care tests at traditional healer locations. This study also has important benefits to healthcare delivery in Uganda as it focuses specifically on early diagnosis of HIV, the leading cause of hospital admissions in this country. The primary and secondary outcomes of the proposed intervention seek to improve health in these regions such that morbidity and mortality are decreased as a result of linkage to outpatient care. The proposed study has the potential to improve rates of HIV testing throughout Uganda, reduce HIV transmission and improve linkage to care. People from other African countries who utilize the services of traditional healers may benefit in the future from the knowledge gained in this study. The results of this study may be expanded to improve access to HIV testing among adults in Uganda and other similar settings. Outcomes will be used to better understand factors influencing engagement with HIV services in endemic areas, where traditional medicine is commonly used. We also hope that the Community Advisory Board formation will facilitate positive, ongoing relationships between healers, biomedical providers, and patients.

8. HUMAN SUBJECTS

8.1 Problems Anticipated:

8.1.2 Psychological risks: For Aim 1, some participants may find it distressing to discuss past HIV testing behaviors, their healthcare seeking trajectory, or experiences with biomedical providers. All study staff will be trained not press participants to answer questions or discuss information that seem to be distressing to them, and to terminate sessions if the participant is overly distressed, fatigued, or frustrated by the effort. In the event that clinically significant depressive symptoms, suicidality, or other psychiatric conditions are noted, the staff will be

instructed to report any incidents or concerns to [name], who will assess the participant, offer needed support or arrange for appropriate referral to a counselor or community service provider. In addition, the PI, and all team members have completed Human Subjects Training and Certification Program or equivalent certification at their institution. Dr.

[name] has had experience conducting social science research among international, marginalized populations and received previous training in the ethical issues that may arise, and procedures utilized to handle protection against risks. [name] has years of experience conducting confidential and interviews regarding sensitive topics among socially marginalized and key populations. All study staff will receive extensive human subjects/research ethics training, including the need for complete confidentiality and to approach questions with sensitivity and in a supportive manner and to provide appropriate referrals when needed.

Qualitative interviews will be terminated if the participant is too distressed, too fatigued, or too frustrated by the effort. In the event that significant depression symptoms or suicidality are noted, the staff will be instructed to follow procedures in the safety protocol, which include immediately contacting [name] to arrange referral to appropriate service agencies at MUST or within the community, and reporting incidents or concerns to the US-based PI, [name].

It is possible that participants may be identified by others as receiving HIV testing, including healthcare personnel, or sexual partners, or become the subject of HIV-related stigma through participating in this study. In addition, any time a person receives a new diagnosis of being HIV-infected there is a possibility that they will be exposed to stigma from family, partners and other members in their community; external stigma in these cases may involve rejection, estrangement, loss of employment or harassment³². Internal stigma may also develop, resulting in shame, depression, and psychological isolation. For women, being HIV-infected may be associated with higher risk of experiencing intimate partner violence. We will work with healers and HIV clinic staff to educate the community to lessen stigma against HIV. Healers will provide post-test counseling for all participants, which will include resources to support their psychosocial health, and provide resources for partners and family members.

8.1.3 HIV test related discomfort: The Oraquick testing process is non-invasive and produces results based on oral fluid samples. We do not anticipate any physical discomfort as a result of the tests administered in the intervention.

8.1.4 Possibility of false HIV test results: Given the high specificity and sensitivity of the rapid tests (99.9% specificity and 91.6% sensitivity), false positives and negatives are unlikely. Participants with positive rapid HIV tests will be referred to the Mbarara Referral Hospital HIV clinic for confirmatory testing, and where they will have CD4 testing and subsequent clinical evaluation. They will be provided specific instructions on how to get there and what to do when they arrive. Healers in the intervention arm will undergo training prior to trial implementation to ensure they are delivering the point of care tests correctly. We note that these point of care tests have been validated for use among laypersons, with extremely high sensitivity/specificity. Research assistants will work with intervention arm healers every few days to ensure testing procedures are followed. Patients with positive HIV testing will be directed to the Mbarara Referral Hospital HIV clinic for confirmatory testing. Patients with negative HIV tests will be counseled to follow up in 3-6 months for re-testing, as is standard protocol according to Ugandan HIV testing guidelines.

8.1.5 Loss of confidentiality: Though this study will include both HIV-infected and non-infected adults, it is possible that participants may be identified by others, including healthcare personnel, as being HIV infected by participating in this study. We will safeguard against this by

conducting interviews, recruitment, and point-of-care testing in private locations. All subject data will be de-identified using a study identification number consisting of a unique code unrelated to any patient identifying information, as per Good Clinical Practice guidelines. Any identifiers linked to the participant will be secured and only available to study staff, to ensure subject confidentiality. Study data will be stored in a locked room at MUST, and on a password protected, encrypted computer. Access to study data will be limited to study staff only. No personally identifiable information will be available during data coding, organization, analysis, or publication. NIMR computers and servers are protected by firewall protection and are only accessible with a password. Study staff will be trained in Good Clinical Practice regarding maintaining confidentiality. We will provide intensive counseling and education to all participants on the importance of confidentiality. In keeping with Ugandan Ministry of Health policy, MUST and Mbarara Regional Referral Hospital does not divulge individual HIV or other results to any third party.

For monthly follow up in Aim 3, study staff will contact the participant via mobile phone. They will be instructed not to discuss anything related to the study except with the participant. They may visit the participant's home if unable to contact via phone numbers provided. For this, they will wear unmarked clothes and not speak about HIV or the study with anyone, except in private with the participant. Participants will be asked to report any breeches in confidentiality, and these will be reported to the IRBs.

8.2 Reasonableness of risks: The research procedures are minimally invasive and present low risks to the study participants. The possible risks include the possibility that participants will become emotionally distressed during the interview process and the potential loss of confidentiality. We have described procedures for dealing with emotional distress or threats to harm self/others, and for minimizing the risk of loss of confidentiality, if it should arise. Given the minimal risks and the safeguards that will be put in place, we believe that the importance of the knowledge to be gained outweighs the potential risks to the subjects involved.

8.3 Obtaining Informed Consent: Written and verbal informed consent will be completed for each participant. During informed consent, the research assistant and potential participant will find a suitable, private location. All potential participants will be told that information gathered in the study is confidential, voluntary, and they are free to take breaks or terminate their participation at any time. A written copy of the informed consent form will be presented in Runyankole or English, depending on the preference of the potential participant. This form will be reviewed orally, and potential participants given opportunity to ask questions. The research assistant will pause after each section and check for understanding by asking the potential participant to describe critical points in his/her own words. If the potential participant agrees to participate, written consent will be documented via signatures from both the research assistant and participant. For those unable to write, they will be allowed to place a thumbprint or "X", with a witness co-signing to ensure proper methods of informed consent have been followed. Each research aim of the study will have its own consent form. Please see those documents attached to this application. No additional consent is necessary. Traditional Healers are considered to have special roles in their communities, as trusted authorities on health, culture and relationships³³ and should be considered key stakeholders for any community-based interventions. As such, their participation and support of this project is highly regarded within specific cultural context. However, this support does not tacitly provide community consent. We will require individual, informed consent for all participants.

The research assistant will review the consent for orally and pause after each section in the consent form to check for understanding by asking the potential participant to describe critical

points in his/her own words. The research staff who will be responsible for obtaining informed consent will assess whether the potential participant has understood the study and consent form by asking key questions (e.g., “How much time will this take you?”; “What are the possible benefits for you?”). Because it is possible that some participants may be cognitively impaired, or they may not initially understand this second consent process, we will test all potential participants for their comprehension of critical in the consent form. Errors will be corrected, and these potential participants will then be asked if they need further clarification. If, after further attempts to clarify any misunderstandings, we determine that they may not fully comprehend the critical aspects of the study, they will not be enrolled.

The vast majority of participants will be non-English speaking, as the primary language in this region is Runyankole. A written copy of the informed consent form will be presented in Runyankole or English, depending on the preference of the potential participant. This form will be reviewed orally, and potential participants given opportunity to ask questions. In addition, we anticipate a significant proportion of potential participants will have low literacy. For those unable to write, they will be allowed to place a thumbprint or “X”, with a witness co-signing to ensure proper methods of informed consent have been followed.

Informed consent documents will be retained in locked filing cabinets and storerooms, accessible only to senior investigators or designated study staff. All study logs are identified by study ID numbers, and names are removed. All computerized databases will only contain study ID numbers. The lists linking study numbers to names are kept separately in a password protected computer, accessible only to PI, Co-Investigator, and Project Manager. Clinicians and counselors have received training on the need to maintain full confidentiality of client data.

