5. STUDY PROCEDURES

5.1 Intervention arm: Healers assigned to the intervention arm (N=10) will attend a half-day training session prior to trial initiation, led by District HIV clinic staff. This training session will demonstrate proper use and disposal of the point-of-care HIV testing kit and provide training regarding patient pre- and post-test counseling. Healers will be instructed to discuss the benefits of linking to HIV care, including importance of initiating treatment for HIV infection, reducing possible transmission to others, and health benefits of starting ART early, as part of post-test counseling. In addition, this training session will discuss resources available at the ISS clinic, including mental health counselors, family and partner support groups, counselors trained to discuss serostatus disclosure strategies, and reproductive health counselors. Supplies for point-of-care HIV testing and biohazard-compliant disposal will be provided to healers at the start of the trial. HIV 1/2 antibody point of care test (Oraquick[©]) will be administered to participants who agree to test. This test is non-invasive, conducted using oral fluids (rather than whole blood), and is FDA-approved for adult use, with results in 20 minutes. Test results are clearly marked with lines, rather than letters or numbers; this test is validated for use by non-medical personnel, with 99.9% specificity and 91.6% sensitivity. Clients with positive tests will be referred to the HIV clinic for Western Blot confirmation, and linkage to care. Following the healer visit, participants will be contacted once per month, for a period of 3 months, to assess for POC test results, and linkage to care for those who test HIV+.

5.2 Control arm: Control arm healers (N=10) will participate in a half-day session prior to trial initiation, led by District HIV clinic staff. This educational session will discuss WHO and Ministry of Health guidelines for HIV testing, who should receive HIV testing and how often, and where to receive it. Participating patients of healers will then receive “enhanced standard of care” as part of the control arm of the trial. Following the visit, study staff will contact the client once per month, for 3 months, to assess for HIV testing since enrollment in the study.

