6. STATISTICAL CONSIDERATIONS

6.1 Outcomes: The primary outcome for this Aim is *rate of HIV testing among TH clients*. Secondary outcomes will include i) *new HIV diagnoses among TH clients*, ii) *patients with +HIV test who successfully link to HIV care in 3 months*³⁰, and iii) variables that predict HIV testing. The results of this Aim are central to demonstrating feasibility for a subsequent R01 proposal.

6.2 Analysis plan: Descriptive statistics will characterize participants and summarize the data. A multi-level logistic regression model – with individual clients in level 1 nested within healers in level 2 – will be used to calculate the odds ratio for primary outcomes within three months in the intervention compared with the control arms. Adjusted analyses will be conducted as secondary or sensitivity analyses using multivariable, multi-level analyses for both binary and continuous variables. All analyses will be performed in R software.

6.3 Intervention evaluation: 3 months following enrollment, all participants will be contacted for an exit survey to understand experiences of participation in the study, undergoing HIV testing, or deciding not to test. In-depth interviews will be conducted with participating healers at the close of the intervention to obtain feedback on delivering POC testing at their practice locations and assess how the study may have impacted their beliefs and practices.

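### Social harms after a new HIV diagnosis are named as risks, but the protocol describes no systematic or timely way of asking participants about them

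*Combined protocol and SAP*

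**What the plan says.** **Harms named.** Section 8.1.2 says of people newly diagnosed that "external stigma in these cases may involve rejection, estrangement, loss of employment or harassment". It mentions internal stigma as well, and then: "For women, being HIV-infected may be associated with higher risk of experiencing intimate partner violence".

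**Monthly contacts.** Participants are contacted once a month for 3 months. In the intervention arm (5.1) the purpose is "to assess for POC test results, and linkage to care for those who test HIV"-positive. In the control arm (5.2) it is "to assess for HIV testing since enrollment in the study".

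**Exit survey.** Section 6.3 plans, at 3 months and for all participants, an "exit survey to understand experiences of participation in the study, undergoing HIV testing, or deciding not to test".

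**Safety reporting.** The procedure in 7.1 and 8.1.2 starts when staff note marked depression or suicidality. Section 7.4 says "Project staff will report emotionally distressed participants to" named investigators. It also covers complaints, confidentiality violations and any serious problem or adverse event, with a report within 48 hours. Section 8.1.5 adds one prompted item: "Participants will be asked to report any breeches in confidentiality, and these will be reported to the IRBs".

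**Risk summary.** Section 8.2 states: "The possible risks include the possibility that participants will become emotionally distressed during the interview process and the potential loss of confidentiality". It goes on to call the risks minimal. Section 7.3 gives minimal risk as the reason for having no stopping rules.

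**The concern.** New diagnoses are a secondary endpoint, so the intervention is meant to produce the very situation in which 8.1.2 expects these harms. They would mostly arise at home or at work after the healer visit, where staff cannot see them. People often do not volunteer partner violence or abandonment unless asked.

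Two things are at stake. A participant harmed in the first month has no described prompt that would bring the event to staff and so to the referral services the protocol already provides. And the pilot is meant to support a larger cluster-randomised trial (sections 1 and 9). A low count of social harms would be read as evidence of safety, although the protocol gives no ground for thinking that harms which occurred would have been recorded.

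**Working it through.** **Step 1. Set each named harm against each channel that could record it.**

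| Channel | Section | Asks about the 8.1.2 social harms? | Timing |
|---|---|---|---|
| Monthly contact, intervention | 5.1 | Not stated; purposes are results and linkage | Months 1 to 3 |
| Monthly contact, control | 5.2 | Not stated; purpose is testing since enrollment | Months 1 to 3 |
| Exit survey | 6.3 | Not named; general experience of taking part and of testing | Once, at 3 months |
| Prompted report | 8.1.5 | Confidentiality breaches only | Not stated |
| Safety procedure | 7.1, 8.1.2 | Starts when depression or suicidality is noted | When noted |
| Adverse event report | 7.4 | Can receive any serious problem; no solicitation described | Within 48 hours |

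The receiving end of the pathway is broad enough. What the text lacks is a step that asks.

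**Step 2. Size of the exposed group.** Section 4.4 gives 250 enrolled, 90% uptake and 9% prevalence: 250 × 0.90 × 0.09 = 20.25, which reproduces the plan's figure of at least 20. With the test performance in 5.1 (sensitivity 91.6%, specificity 99.9%):

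- true positives: 225 × 0.09 × 0.916 = 18.55
- false positives: 225 × 0.91 × 0.001 = 0.20
- test-positive clients: 18.55 + 0.20 = 18.75

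So 19 to 20 clients would be told of a positive result. This carries the 9% forward unchanged. Section 4.1 excludes people with known HIV; if the 9% includes people already diagnosed, the number would be smaller. The documents do not say.

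**Step 3. What incomplete ascertainment would do (illustration only).** The documents give no harm rate and no capture rate, so both are assumed here. With n = 20, harm rate r and fraction surfacing s, the chance of recording at least one case is 1 − (1 − r·s)^20.

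| Assumed harm rate | All surface | Half surface | A quarter surface |
|---|---|---|---|
| 5% | 64% | 40% | 22% |
| 10% | 88% | 64% | 40% |
| 20% | 99% | 88% | 64% |

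The first column is close to the chance that a harm occurs at all (with 19 clients it is 62%, 86% and 99%). The other two columns show the effect of capture: at a 10% rate, the chance of seeing any case falls from 88% to 40% if only a quarter surface. Even with full ascertainment, zero cases among 20 would be compatible with a rate up to 1 − 0.05^(1/20) = 13.9% (one-sided 95% limit). With unknown capture, no such limit can be given.

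**Step 4. Compare the risk summary with the risk section.** Section 8.2 lists interview distress and loss of confidentiality. Section 8.1.2 lists those kinds of risk and, in addition, partner violence, rejection and job loss. The safeguards that 8.2 relies on concern distress, threats to harm self or others, and confidentiality; violence done to a participant by a partner is not mentioned.

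**The case against.** A reader might infer that these harms can come to light only if a participant volunteers them or staff happen to notice, and that none of the scheduled contacts asks. The documents do not support that. The exit survey in 6.3 is initiated by staff, reaches all participants and covers their experience of the study and of testing, so it could bring such harms out. The wording in 5.1 and 5.2 states a purpose and is not a closed script. The contact forms, the exit survey and the separate safety protocol are not in the documents and may contain suitable items. What can be said is that the protocol text does not say they ask.

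A reader might also infer that 7.4 is too narrow, or that 8.2 denies these risks and so undermines the decision in 7.3 to have no stopping rules. Neither holds. Section 7.4 extends to any serious problem or adverse event. The list in 8.2 is introduced as what the risks include, so it is not exhaustive, and 7.3 appeals to minimal risk in general without relying on that list.

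The protocol also offers real support: post-test counselling with psychosocial resources (8.1.2), clinic counsellors and partner support groups (5.1), disclosure counselling (7.2) and gender-matched home visitors (5.3). This reduces harm but does not measure it.

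Finally, asking by phone is not free of risk. Section 5.3 cites 65% phone ownership, with a backup contact's phone or a home visit as fallback, so a partner or relative may be within hearing. That objection stands and shapes the fix.

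**Conclusion.** The point holds as a gap in active, timely ascertainment. The harms in 8.1.2 have a place to be reported but no described question that would find them, apart from a general survey at the end of follow-up with no stated route to 7.4. Social harms are therefore likely to be under-recorded, and those found may be found late.

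The exposed group is about 19 to 20 clients on the plan's own inputs. The number of harms missed cannot be derived from the documents; the percentages in the tables rest on assumed harm and capture rates and show direction only. The conclusion also assumes that the unseen questionnaires contain no more than the protocol describes. If they do contain such items, the remedy reduces to saying so in the protocol and linking the answers to 7.4.

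The primary outcome and its analysis are unaffected. The change is worth making because it improves participant safety and the pilot's harm data at low cost.

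**What to change.** 1. Add to each monthly contact and to the exit survey, in both arms, a short fixed set of questions covering the social harms named in 8.1.2: partner violence or threats, rejection or estrangement, loss of work, and harassment. The same items in both arms make the counts comparable.
2. Ask them only after the participant confirms privacy, never through a backup contact and never with others present. Record when the questions could not be asked, so that missing answers are not counted as no harm.
3. Send any positive answer into the existing 7.4 report, on its 48-hour timing, and the existing referral pathway.
4. Tabulate the counts by arm, with the number of participants asked as the denominator.
5. Reconcile the 8.2 risk summary with 8.1.2.

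**Cost.** No new visits: up to 500 × 3 = 1,500 monthly contacts are already scheduled. It needs revised forms, brief staff training and a privacy check at each contact. Recorded harms will rise, which should be stated in advance so that the rise is read as better capture.
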